To further engage YEH, we will meet them "where they are"⁸ and implement the intervention in collaboration with existing health and social service providers. This strategy is particularly important given that past month use of a drop-in center predicts HIV/STI testing⁷⁷ and being linked to a drop-in center is significantly associated with increased service utilization ($p < 0.01$) and improved HIV-related outcomes ($p < 0.001$).⁴⁹ These findings support the potential of delivering HIV prevention in drop-in centers and shelters to connect healthcare underutilizing YEH. Moreover, drop-in centers may be the preferred HIV prevention service location of YEH.⁴⁹ By integrating the delivery of NCM4HIV into already established social services, we can enhance HIV prevention while improving access to mental health, substance use, and housing services. Because these service agencies also conduct weekly street outreach where we can recruit youth, we anticipate reaching disconnected youth who have yet to present for health or social services.

Innovation

While NCM and MI are established methods for behavioral change and care engagement among high-risk populations, nurses are underutilized as behavioral change agents.⁷⁸ This early-stage and new-investigator R01 is innovative in the following ways: (1) it will take best advantage of the underutilized role of nurses, American's most trusted professionals, in the HIV prevention team; (2) nurse provision of HIV prevention services will remove the need to refer YEH to other medical personnel, which can decrease compliance; (3) enhancing NCM with MI and behavioral feedback to increase YEHs' motivation for adopting HIV prevention behaviors; (4) addressing the full continuum of behavioral and biomedical HIV prevention with YEH; and (5) the intervention can be applied to improve any existing YEH HIV prevention program.

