Inclusion Criteria. We will limit our sample to YEH ages 16-25 years to align with adolescent brain development,^{4,5} risk behavior,⁶ YEH literature, the current clinical and FDA guidelines for PrEP and nPEP use, and the extant literature suggesting that experiencing homelessness as a young adult under 26 is associated with heightened sexual risk behaviors and substance use.⁷ Individuals will be included if they (1) engage in high-risk sexual activity or intravenous drug use, (2) are 16-25 years old, (3) speak English, (4) are experiencing homelessness, and (5) are not planning to move out of the metro area during the study. High-risk sexual activity will be defined as having condomless vaginal or anal sex in the past 6 months. While Houston has a high Hispanic population, only 1 of the 434 youth from Youth Count 2.0 preferred to take the survey in Spanish, and the large majority of Hispanic YEH in Houston prefer English. Therefore, we do not anticipate excluding otherwise eligible youth based on language by limiting to English speaking youth. Experiencing homelessness will be defined as having slept on the streets, in a place not meant for habitation, in a shelter, hotel/motel, or with someone where they cannot stay for more than 30 days (e.g., couch surfing). YEH may stay in emergency shelters or on the streets (e.g., parks and tent cities), in abandoned or vacant buildings or apartments, temporarily with friends, family, or acquaintances, or in rented hotel/motel rooms⁸ and go to great lengths to stay hidden from the dangers of victimization.⁹ This broader definition of homelessness aligns with the McKinney-Vento Homeless Assistance Act of 1987 which allows us to account for the transiency and instability of housing experienced by YEH, and increases the generalizability of the study findings. If a youth has low literacy based on the REALM-SF (scores < 4) they will be excluded due to the need to read at a 4th grade level for the daily dairies.² Only 2 youth from Youth Count 2.0 were excluded based on their literacy level. While youth could access the survey using the audio-assisted feature of REDCap regardless of their literacy level, they may

not be able to read the daily diaries if they were assigned to the intervention arm. This set of criteria were used successfully in our prior studies.

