identify youth at the site each day who may be eligible. Research staff will also encourage youth to follow the study social media pages for updated information about how to be involved with the study. We will recruit participants three days a week during regular business hours at the shelter and drop-in centers and during street outreach. The research staff will maintain a consistent presence at the agencies and will approach young people who present. In the event that the common room in the shelter or drop-in center is crowded, they will ask to speak to identified youth in a private office. The research staff will explain the study and complete the informed consent process with interested youth. All prospective participants will be assured that study participation will in no way affect their health and social services. Informed consent and contact information will be obtained from participants. For minors between 16-17 years of age who are seeking homeless services and are otherwise considered emancipated, we will also obtain written informed consent to participate in the study and seek a waiver of parental consent for minors based on Federal Rule 45 CFR 46.408(c). We have successfully obtained this waiver of parental consent for minors experiencing homelessness in our prior studies. **Consent to Access Medical Records.** During the informed consent process, study participants will give permission to access their medical records using the HIPAA Authorization Form for study purposes.

Consent and Protection of Human Subjects.

A step-wise screening process will be followed. First, we will screen potential participants for eligibility using a REDCap form. The survey will ask age, if they are sexually active, and if they are receiving homeless youth services. We will also administer the Rapid Estimate of Adult Literacy in Medicine-Short Form (REALM-SF) and enter the score into the eligibility form.^{2,3} See Appendix for REALM-SF. If they are within the age range, are receiving homeless services, and score greater than or equal to 4, then we will consent the participant.

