Appendix A: REALM-SF

Transience Resilience Cocaine Pregnancy Satisfied Temporary Identity Hepatitis Victimization

Instructions for Administering the REALM-SF

1. Show the youth the above words on the tablet (or a card).
2. Say: "I want to see what format will work best for you to do the survey. I want to hear you read as many words as you can from this list. Begin with the first word and read aloud. When you come to a word you cannot read, do the best you can or say, 'blank' and go on to the next word."
3. If the youth takes more than 5 seconds on a word, say "blank" and point to the next word, if necessary, to move the youth along. If the youth begins to miss every word, have him or her pronounce only known words.
4. Enter REALM SCORE in box below

(Score needed for youth to take survey alone=4; Interviewer: if youth scores 0,1,2,or 3 please administer survey with youth)

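### The screening and consent rule contradicts the inclusion criteria: it omits HIV risk, sleeping place and moving plans, and adds receipt of homeless services

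*Combined protocol and SAP*

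**What the plan says.** **Study Population, Inclusion Criteria.** "Individuals will be included if they (1) engage in high-risk sexual activity or intravenous drug use", are aged 16-25, speak English, and meet the last two conditions: "4) are experiencing homelessness, and (5) are not planning to move out of the metro area during the study". Two terms are defined. On sexual risk: "High-risk sexual activity will be defined as having condomless vaginal or anal sex in the past 6 months". On housing: "Experiencing homelessness will be defined as having slept on the streets, in a place not meant for habitation", with shelters, hotels or motels, and short stays with others also counting. Service use is not part of that definition. A REALM-SF score below 4 excludes, and Exclusion Criteria repeats this.

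**Consent and Protection of Human Subjects.** The REDCap screening form is described as asking age, whether the youth is sexually active, and whether homeless youth services are being received. REALM-SF is added. The decision rule covers youth in the age range who "are receiving homeless services, and score greater than or equal to 4, then we will consent the participant".

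**Target population.** Background Information says of street outreach: "we anticipate reaching disconnected youth who have yet to present for health or social services". The Recruitment section gives representation of both connected and disconnected youth as a reason for its range of recruitment sources, and links it to generalizability.

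**Appendix A.** The REALM-SF instructions give a score of 4 as the threshold for taking the survey alone, and add: "if youth scores 0,1,2,or 3 please administer survey with youth".

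**The concern.** Two parts of one protocol decide who enters the trial, and they give different answers. The section that staff would follow at the point of screening is the shorter one. It leaves out the criterion that makes this a trial of HIV prevention in at-risk youth, and it puts service receipt in place of homelessness.

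Two things are at stake. The first is who the results describe: the rule can admit youth whom the inclusion list rejects, and reject youth whom the list accepts and the trial says it wants to reach. The second is the treatment contrast. Condom use and PrEP uptake are components of the primary endpoint. Youth with no condomless sex have little or none to reduce, and youth without HIV risk have less reason to start PrEP, so enrolling them would pull both effects toward zero.

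**Working it through.** The documents attach no figure to this point, so the check is a comparison of text.

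**Step 1. Criterion by criterion.**

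| Criterion | Inclusion/Exclusion Criteria | Screening form as described | Consent rule |
|---|---|---|---|
| HIV risk | Condomless vaginal or anal sex in past 6 months, or intravenous drug use | Only whether sexually active | Not used |
| Age | 16-25 | Asked | Used |
| Language | English | Not listed | Not used (the reading test touches it indirectly) |
| Homelessness | By where the youth has slept | Receipt of services asked instead | Receipt of services required |
| Moving | No plan to leave the metro area | Not listed | Not used |
| Literacy | REALM-SF below 4 excluded | Administered | At least 4 required |

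Age and literacy agree. The other four do not.

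**Step 2. What the mismatch allows.**

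- A 17-year-old service user who reads well, has had no condomless sex in 6 months and does not inject drugs passes the consent rule and fails the inclusion list. So does one who plans to move away, or whose sleeping place does not meet the definition.
- A 20-year-old who sleeps on the street, has had condomless sex in the past 6 months and receives no services meets the inclusion list and fails the consent rule.

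**Step 3. Is there a later check?** The places where one could sit are these:

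- *HIV/STI Test Specimens* adds a rapid HIV test to eligibility screening. It does not check risk behaviour, housing or moving plans.
- *Exclusion Criteria* defers intoxicated or acutely distressed youth to a later screening. This adds no criterion.
- *Informed Consent Procedures*, remote route: the screener tells the youth whether they are eligible before consent starts, by reference to the current protocol.
- *Recruitment* describes completed enrolment as consent, baseline data, then group assignment and phone. No eligibility decision is placed between these.
- *HIV Risk Profile and PrEP Eligibility Assessment* does ask about risk behaviour, but in the nurse sessions, after randomisation, in the intervention arm, and to judge suitability for PrEP.
- The survey condom items described under *Measures* cover last sex and the past 3 months, a shorter period than the 6 months in the criterion.

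None of these applies the missing criteria before randomisation.

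**Step 4. Where the screen carries most weight.** Recruitment includes social media advertising aimed at 16-25 year olds in the Houston area. That channel selects neither on homelessness nor on HIV risk, so the screening form has to do so.

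**Step 5. Literacy.** Inclusion Criteria, Exclusion Criteria and the consent rule all keep out youth scoring below 4. Appendix A tells staff how to run the survey with youth scoring 0-3. If the exclusion applies, no such youth would reach the survey.

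**Step 6. Size.** Sizing the effect needs the share of consented youth who fail the inclusion list and the share of eligible youth turned away. The documents give neither, so the size cannot be computed.

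**The case against.** The best defence is that Inclusion Criteria is the governing text and the consent passage is a short summary in an ethics section. Screening is called step-wise, the HIV test is missing from that summary too, the REDCap form is not in the available text, and eligibility under the current protocol can be read as pointing to the inclusion list. This is fair as far as it goes: staff may in practice ask more than the summary lists, and the rule permits ineligible enrolment without proving that it happens. It does not remove the contradiction. The summary states a complete decision rule ending in consent, and no second step that checks the missing items is described anywhere.

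Three stronger readings are tempting, and the documents do not support them.

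- **A reader might infer that disconnected youth are shut out.** Receiving homeless services is not defined. Partner agencies run the street outreach, and outreach contact could be counted as a service. The rule can exclude youth who receive no services; whether it does turns on that missing definition.
- **A reader might infer a computable loss of power** by shrinking the planned 0.55 against 0.40 contrast for an assumed share of youth without condomless sex. Any such share is invented. The plan's simulation already assumes that 79% are sexually active, so about 21% (450 × 0.21 = 94.5 youth) are not, and a further reduction would partly count the same youth twice. A simple single-visit test with 105 and 210 participants starts at 71% power, whereas the plan reports 87% from a repeated-measures simulation, so losses taken from the former do not describe the planned analysis.
- **A reader might infer higher attrition** because moving plans are not asked. Sample Size and Power Calculations bases 70% retention on resources, partnerships, phones and incentives, not on the moving criterion, and calls it conservative against 88-89% in other studies. Baseline and Follow-up Survey Data also provides a remote survey link for youth who leave the area.

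**Conclusion.** Wrong as written. The consent rule and the inclusion criteria cannot both be followed. The rule permits consent of youth without the required risk behaviour, outside the homelessness definition or planning to move, and no later check is described. It can also exclude high-risk homeless youth who receive no services, against the stated aim of including disconnected youth. Appendix A adds a second conflict, over literacy.

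The consequence is a study population that may differ from the one defined, with possible dilution of the condom and PrEP effects. The direction of dilution assumes that some youth without the risk behaviour are in fact enrolled. Its size is unknown, and no power or attrition figure should be attached to it. The finding rests on the protocol text; the REDCap form itself could show that more is asked than is described.

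**What to change.** Rewrite the rule in Consent and Protection of Human Subjects so that it applies the whole inclusion list:

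- condomless vaginal or anal sex in the past 6 months, or intravenous drug use;
- age 16-25;
- English;
- homelessness as defined under Inclusion Criteria, whether or not services are received;
- no plan to leave the metro area;
- REALM-SF of at least 4.

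Put the same items on the REDCap screening form, in person and by phone, and require all of them before consent. If service receipt is still recorded, define it, say whether outreach contact counts, and use it only to describe the sample. Reconcile the Appendix A instruction for scores 0-3 with the literacy exclusion.

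By the Appendix B timeline, recruitment is under way at this version's date. For youth already enrolled, check what the form asked, log as deviations any who did not meet the criteria, and report their number by arm.

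The cost is a few items on an existing form, a wording amendment, and a review of existing screening records.

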This intervention has 2 components: **(1) 6 Face-to-Face NCM Sessions** delivered by a nurse who will assist a participant to generate HIV prevention goal using Motivational Interviewing strategies and conduct an HIV risk profile and eligibility PrEP assessment. The nurse will meet the participant in a non-stigmatizing, trauma-informed way that respects where they are at in their current situation and evokes personal motivation for health promoting behaviors. Sessions are designed to meet the complex, multi-level health and social needs of homeless youth to align with the extant literature demonstrating the strong connection between HIV risk behaviors and mental health, substance use, and housing.¹ Therefore, at each session, the nurse will assess mental health, substance use, and housing needs to establish a plan of care with the participant. The nurse will coordinate health and social service navigation with the social workers at the agencies as needed with permission of the participant. The nurse will review HIV acquisition and transmission risk factors with the participant at each session and inquire about engagement in sexual risk behaviors since the last NCM session. During each NCM session and as needed, youth will complete an HIV risk profile used in the clinic setting to assess for PrEP eligibility based on the extent of behavioral risk. A screening tool developed from the Centers for Disease Control and Prevention 2014 Clinical Practice Guidelines for PrEP use will be used to assess PrEP eligibility based on HIV risk behaviors at the beginning of each NCM session to determine whether recent behaviors warrant PrEP as a possible intervention for HIV prevention. This includes having a HIV-positive sexual partner, recent bacterial STI, a high number of sex partners, a history of inconsistent or no condom use, or commercial sex work, and IV drug use. Houston, TX is considered a high HIV prevalence area and homeless youth are considered a high prevalence network. The nurse will use MI strategies to evoke participant generated HIV prevention goals and strategies. In the event that a participant is unable to attend a session in person, they will be offered the option of attending the session via video chat or phone, or meeting at a public location that is convenient for them such as a neighborhood library. Due to COVID-19, nurse may elect to deliver the intervention via video call depending on current COVID-19 risk level, availability of PPE, health of study staff, health of participant, and location of participant. **(2) Behavioral Feedback.** Each session will entail HIV prevention education (i.e., risk behaviors and prevention strategies) and behavioral goal setting to align the participant's goals with their current behaviors to evoke personal motivation to adopt and maintain HIV prevention strategies. Building on the goal setting of NCM using MI strategies, intervention youth will complete very brief daily diaries on their study-issued phone that populates an interface that provides visual feedback about how one's current behaviors align with their health goals. These daily diaries take less than 5 minutes to complete each day. The nurse then can use this visual to facilitate discussion about the barriers and facilitators that impeded or enhanced one's ability to actualize the uptake and adherence to HIV prevention strategies. The nurses will make monthly booster calls to intervention participants on the study issued phone in months 1-3 following the end of the face-to-face sessions. During this call, the nurse will inquire about the uptake and adherence to the HIV prevention strategies outlined during the NCM sessions, any other needs that they can address for the participant at that time, and will help the participant navigate services as needed.

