One focus of the investigator meetings will be to continuously monitor and develop strategies to prevent adverse reactions, monitor the research staff, and protect data integrity. Accrual data will be reviewed by the team and the UTHealth IRB. The study team will make amendments to the protocol should accrual fall below 15% of the target, or should drop-outs exceed projections by 15%. This will include the addition of recruitment sites.

Statistics

Randomization. Participants will be randomly assigned to the intervention or wait list control arm using a computer-generated blocked 2:1 allocation; 300 participants will be in the intervention arm and 150 will be in the wait list control arm (see Figure 3). Participants will be told which group they are in after completing the baseline survey and will receive a study-issued phone with programmed YEH resources unless they prefer to use their own phone. In this case, the behavioral feedback app will be loaded onto their personal phone for those in the intervention arm, and these youth will be provided with a list of YEH services.

Study Design.

| | Baseline | Intervention | 3 Mon. | 6 Mon. | 9 Mon. | Intervention |
|-------------------|----------------|------------------|----------------|----------------|----------------|--------------|
| Treatment arm | O ₁ | X O ₂ | O ₃ | O ₄ | O ₅ | |
| Wait list control | O ₁ | O ₂ | O ₃ | O ₄ | O ₅ | X |

Sample Size and Power Calculations. The primary endpoint is the efficacy of NCM to increase PrEP and nPEP uptake, HIV testing, STI screening, and condom use. Conservatively assuming an attrition rate of 30% at 9 months, the final sample size will be 315, with the 2:1 randomization allocation providing for 210 participants in the intervention arm and 105 in the control arm. We estimate a retention rate of 70% based on study resources, community partnerships and support, the use of study-issued phones, the use of increasing follow-up incentives. This retention rate is substantially lower than the rate reported for other longitudinal YEH studies that have retained 88-89% ^{13,14} of youth to be very conservative in our retention estimation.

Table1. Outcome Measures by Study Aim

| Construct | Scale/Measure | Alpha |
|-----------------------|---|-------|
| Aim 1 Outcomes | | |
| PrEP/nPEP Uptake | PrEP uptake; nPEP uptake (NCM report, chart review) | NA |
| Condom Use | Youth Risk Behavior Survey; ¹ (condom use at last sex) | NA |

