Participant Tracking. Our team has a strong track record of retaining homeless youth in longitudinal studies. All participants will complete an extensive tracking form at the time of enrollment to collect participant contact information including personal phone number, alternative phone number (e.g., parent, sibling, or peer phone number), case manager phone number and email address, and social media information (e.g., Instagram and Facebook names). Youth will also be asked to sign a UTHealth media release and take a polaroid photo soley for the purpose of verifying participant identity during data collection and gift card distribution. This information is voluntary though youth will be instructed on the utility of providing this information to assist study staff in contacting youth for follow-up over the course of the study. These tracking procedures have been successful in our previous homeless youth studies and are supported by the literature.¹⁰⁻¹⁴ We have a strong participant tracking database in place using the REDCap data management system. To follow-up with participants, the RA will first send participants a text message reminder on their study-issued phone to schedule the in-person survey at 3, 6, and 9 months. In order to improve retention, RAs will inform participants that if they contact the study team to schedule their 3, 6, and 9 month survey first, they will receive an extra \$5 gift card incentive. If the RA is unable to reach the participant by text, they will then call the study phone and other contacts listed on the contact form (e.g. friends, family, and case manager). Finally, RAs will reach out to participants using the private message features on Instagram and Facebook to reach youth. RAs will also be on site at the drop-in center and shelter weekly and therefore be able to meet up with youth who are due for follow-up. Finally, as part of the tracking and consent forms, participants will be asked for permission to contact the social workers and shelter and drop-in center staff in a final attempt to get ahold of the participant if the above methods have not worked. The nurses will also discuss the date of the next sessions and preprogram the calendar of the participant's study-issued phone with the dates of the 3, 6, and 9 month follow-ups. A smartphone calendar reminder will be set for 48 hours prior to the appointment to prompt the participant to call study staff to schedule the visit in the case the RA has not been successful in contacting the participant and scheduling the follow-up visit. The RAs will stay engaged with the homeless youth population by being at the recruitment sites weekly and attending agency events monthly.

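### Calendar pre-programming of follow-up dates is a nurse task with no one named to do it for wait-list controls, so this one retention aid reaches mainly the intervention arm

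*Combined protocol and SAP*

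**What the plan says.** The Participant Tracking section (under Ethics) makes the RAs responsible for arranging follow-up visits, without limit by arm. To begin, "the RA will first send participants a text message reminder on their study-issued phone to schedule the in-person survey". Next, "If the RA is unable to reach the participant by text, they will then call the study phone and other contacts" on the contact form. Private social-media messages, weekly presence at the sites and, as a last attempt, contact through agency staff complete the RA steps.

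One sentence then adds a nurse task: "The nurses will also discuss the date of the next sessions and preprogram the calendar" of the study-issued phone, with the 3-, 6- and 9-month dates. The next sentence is in the passive: "A smartphone calendar reminder will be set for 48 hours prior to the appointment to prompt the participant to call study staff". Its stated purpose is as a fallback, "in the case the RA has not been successful in contacting the participant".

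The design tables (Figure 2, and again under Statistics) place the wait-list arm's intervention after the 9-month assessment. Booster calls are for the intervention arm: "The nurses will make monthly booster calls to intervention participants on the study issued phone in months 1-3" after the face-to-face sessions end.

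Sample Size and Power Calculations starts from "Conservatively assuming an attrition rate of 30% at 9 months" and applies that rate to both arms.

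**The concern.** Booking outcome assessments is a research procedure, not part of the treatment under test, and it should be the same in both arms. Here one piece of it is attached to staff whom only the intervention arm is scheduled to see before the last outcome visit. The reminder is meant for youth the RA has failed to reach, so it acts on those most likely to be lost.

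If loss differs by arm and is related to outcome, the comparisons of self-reported condom use, mental health symptoms, substance use and housing are between differently selected groups. Stating the intent-to-treat principle does not repair that. PrEP/nPEP uptake is less exposed, because it comes from nurse report and chart review.

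**Working it through.** **1. Who does each tracking step, and for whom**
- Text, calls, social media, site presence, agency contacts: RA, participants in general.
- Calendar entry of the 3-, 6- and 9-month dates: nurses. No other role is named anywhere in the documents.
- 48-hour reminder: no role and no arm named. The only calendar entry described for it to attach to is the nurses'.

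**2. Nurse contact before 9 months**
- Intervention arm: six sessions, then three monthly booster calls.
- Control arm: nothing scheduled. Incidental contact is possible, since RNs obtain gonorrhoea and chlamydia results and the nurse case manager links youth who test HIV positive to care (HIV/STI Test Specimens). Nothing connects those contacts to follow-up dates.

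**3. The plan's own retention figures**
450 × 0.70 = 315; 300 × 0.70 = 210; 150 × 0.70 = 105. These reproduce exactly and confirm that equal loss is assumed.

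**4. What unequal loss could look like (the split is an assumption)**
Holding overall loss at 30%: 300·Li + 150·Lc = 0.30 × 450 = 135, where Li and Lc are loss in the intervention and control arms.
- Li = 0.28: Lc = (135 − 84)/150 = 0.34.
- Li = 0.25: Lc = (135 − 75)/150 = 0.40.

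**5. Shift in the arm contrast (the gap is an assumption)**
Let g be the outcome among lost youth minus that among retained youth, the same in both arms. The retained mean equals the full mean minus L × g, so the contrast shifts by (Lc − Li) × g.

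| Loss, intervention v control | g = 0.10 | g = 0.30 |
|---|---|---|
| 28% v 34% | 0.06 × 0.10 = 0.006 | 0.06 × 0.30 = 0.018 |
| 25% v 40% | 0.15 × 0.10 = 0.015 | 0.15 × 0.30 = 0.045 |

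The planned condomless-sex difference is 0.55 − 0.40 = 0.15, so the extremes are 0.006/0.15 = 4% and 0.045/0.15 = 30% of it. The sign depends on whether lost youth do worse or better than those retained.

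**6. A second route**
Take no true effect, with condomless sex at p = 0.55 in both arms, and let r be the retention of youth with condomless sex relative to those without. The observed proportion is p·r/(p·r + 1 − p).
- r equal in both arms: no bias, whatever the loss.
- r = 0.9 v 0.8: 0.524 v 0.494, about 2.9 points.
- r = 1.0 v 0.8: 0.550 v 0.494, about 5.6 points.

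Swapping the arms reverses the sign.

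**7. Power**
For a simple two-proportion test of 0.55 v 0.40 among the 79% sexually active (two-sided 0.05 assumed), power falls from 0.612 with equal 30% loss to 0.576 at 25% v 40%. This is not the plan's mixed-model simulation and serves only to compare the two splits. The cost in power is small; bias is what matters.

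**8. Would the plan notice or handle it?**
- The amendment trigger is drop-outs exceeding projections by 15%. A 25%/40% split still totals 30%, so it would look on target.
- The Safety Monitoring Committee receives completion of scheduled follow-ups, with no breakdown by arm stated.
- The Analysis Plan expects little missing data, imputes missing items within instruments, and gives no method for missed visits or for loss that differs by arm.

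**The case against.** A reader might infer that follow-up scheduling as a whole has been given to the nurses. It has not: the RAs do it in both arms through several channels, and the nurse step is an addition.

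A reader might also infer that controls get no 48-hour reminder. The documents do not say so. The sentence names no role or arm, and a site could set the reminder for everyone. It remains true that no text provides for this in controls.

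Nor is it right that only intervention youth meet nurses. That holds for scheduled sessions and calls, but some controls may hear from a nurse about results or linkage to care.

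The strongest objection concerns size. Nothing in the documents shows that a calendar entry, added to everything the RAs do, changes retention. The illustrative figures multiply two assumptions, and the 30%-of-effect value is the top of both. Sessions, booster calls and diaries also create unequal contact, so any difference in loss would have several causes. It would be wrong to say that the plan makes loss unequal by design.

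The nurses' role also has a practical reason. Surveys are timed from the end of the intervention, and the nurse knows when the sessions end. That affects how the fix should be written, but does not explain why controls are left out.

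The step names only the study-issued phone, while the Randomization paragraph lets youth use their own. That gap is not specific to an arm and is no evidence of imbalance.

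**Conclusion.** The point holds in a limited form. Calendar pre-programming of the outcome-visit dates is written as a nurse task, no one is assigned to it for controls, and controls have no scheduled nurse contact before 9 months. Followed literally, this aid, and probably its reminder, reaches mainly the intervention arm. It is an avoidable difference in a research procedure, in a plan that expects 30% loss, assumes it equal and has no stated method for missed visits.

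Differential dropout is a possible consequence, not a demonstrated one. The 0.6 to 4.5 point range (up to 5.6 by the second route) rests on assumed loss splits, outcome gaps and retention ratios that are not in the documents. It describes unequal loss from all causes, not the effect of this step. This is a cheap improvement, not a flaw that undermines the trial.

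**What to change.** In Participant Tracking, replace the nurse sentence with wording to this effect:

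> At enrolment, the RA will enter target dates for all follow-up assessments, each with a 48-hour reminder, in the calendar of whichever phone the participant will use, for every participant in both arms. Target dates will be counted from the same time anchor in both arms. The RA will update them at the immediate-post survey. Nurses will schedule only their own sessions and calls.

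The entries have to be target dates because surveys are timed post intervention and the end of the sessions is not known at enrolment. A stated common anchor also gives controls, who have no intervention to count from, a defined schedule. If the immediate-post survey is missed, the target dates remain in place.

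Report follow-up completion by arm and visit, both to the Safety Monitoring Committee and in the results.

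Cost: a few minutes of RA time per participant, at an enrolment visit where group assignment and phone issue already take place, and again at the immediate-post survey. No new staff or visits are needed. Unequal contact from sessions, booster calls and diaries will remain, because it is part of the intervention; this change removes only the part that is not.
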